### 13.5 Secondary Efficacy Analyses

The secondary efficacy endpoints are listed in [Section 2.1.2](#). Changes from Baseline will be summarized by treatment group using continuous summary statistics and analyzed using an analysis of covariance (ANCOVA) model with terms for baseline value, treatment, and analysis center. [REDACTED]

[REDACTED] Least squares (LS) mean for each treatment group and for the difference between treatment groups will be presented from the model together with two-sided p-values and 95% CIs. [REDACTED]

[REDACTED].

Specifically, the global SANDE as well as SANDE severity and SANDE frequency scores will be analyzed:

- With methodology in Estimand 1 ([Section 2.3.1](#)) using ITT population;

All other secondary efficacy endpoint will be analyzed:

- With methodology in Estimand 1 ([Section 2.3.1](#)) using ITT population;

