Key Inclusion Criteria Subjects must meet all of the following criteria to enter into the study: 

• Male or female, 30 years of age or older at the Screening visit

• Have a previous history of DED, clinician diagnosed or patient reported, within the previous 6 months prior to the Screening visit

• Have used and/or desired to use artificial tears for DED symptoms within 2 months prior to the Screening visit

• Both of the following signs of DED in the same eye:

• Total corneal fluorescein staining score of <math>\geq 2</math> and <math>\leq 15</math> based on the modified NEI grading scheme, with no one region scoring <math>> 3</math> in at least 1 eye at the Screening visit only

- Anesthetized Schirmer test score  $\geq 2$  and  $< 10$  mm/5 min in at least 1 eye and the same eye must qualify at both Screening and Baseline visits
- A score of  $\geq 50$  based on Ocular Discomfort Score (ODS) assessed on a Visual Analog Scale (VAS) at both the Screening and Baseline visits
- A score of  $\geq 50$  based on SANDE (Symptoms Assessment iN Dry Eye) at both the Screening and Baseline visits
- Increase in the signs and symptoms of DED based on the CAE exposure at the Screening visit only demonstrated by:
  - a.  $\geq 1$ -point increase in inferior region corneal staining score (assessed using sodium fluorescein staining) in at least 1 eye based on the Ora Calibra® grading scale after the 90 minute CAE® exposure
  - b. Ora Calibra ODS score  $\geq 3$  at 2 or more consecutive time points in at least 1 eye during CAE® exposure within  $\leq 20$  minutes of entering the CAE® (if a subject has an ocular discomfort rating of 3 at time 0 for an eye, the subject must report an ocular discomfort rating of 4 for 2 consecutive measurements for that eye within  $\leq 20$  minutes of entering the CAE)
- Corrected visual acuity equal to or better than logMar  $+0.7$  (Snellen equivalent equal to or better than 20/100), as assessed by Early Treatment of Diabetic Retinopathy Study (ETDRS) scale in both eyes at both the Screening and Baseline visits

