#### **9.5.4 Secondary Efficacy Analyses**

The secondary efficacy analyses will be conducted in the ITT population with intercurrent events handled as described in the missing data section. Changes from Baseline will be summarized by treatment group using continuous summary statistics and analyzed using an ANCOVA model with terms for Baseline value, treatment, and site. In addition, the study site by treatment interaction will be explored in a separate model to evaluate how the treatment effect may differ across study sites. Least squares mean for each treatment group and for the difference between treatment groups will be presented from the model together with two-sided p-values and 95% confidence intervals.

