#### 8.4 Definition of Baseline

Baseline is defined as the last non-missing measure prior to the initiation of randomized study intervention.

- The efficacy endpoint baseline will be the Baseline (Day 1) measurement. Screening visit and unscheduled visit measurements if any prior to the initiation of randomized study intervention **will not be considered** for baseline even when Baseline (Day 1) measurement is missing.
- For unanesthetized Schirmer test measures taken at both pre-drop and post-drop, the pre-drop measure at Baseline (Day 1) will be the baseline for primary and secondary analyses as specified

in Sections 2.1.1 and 2.1.2, [REDACTED]  
[REDACTED]

- The safety endpoint baseline will be the Baseline (Day 1) measurement. When Baseline (Day 1) measurement is missing, the last non-missing measurement from Screening visit and unscheduled visit measurements prior to the initiation of randomized study intervention **will be considered** for baseline.

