#### **13.2 Secondary Efficacy Assessments**

##### **13.2.1 SYMPTOM ASSESSMENT IN DRY EYE QUESTIONNAIRE**

The SANDE questionnaire is comprised of 2 unique VASs to assess the frequency and severity of DED symptoms. Subjects will be asked to complete the SANDE to rate both the frequency and severity of DED symptoms for both eyes together. Each of the two questions will be accompanied by a VAS. The assessment line length of the scale will be 100 mm and will be similar to the following depiction (Figure 3). Higher scores indicate greater frequency or severity of symptoms of dryness and/or irritation. In addition, a global SANDE score is also collected in the eCRF, which is calculated by multiplying the frequency score by the severity score and obtaining the square root rounded to the nearest whole number.

The SANDE will be administered at Screening, Baseline (Day 1), and Days 7, 14, 28, and 90. The frequency, severity and global SANDE score will be summarized.

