### 13.2.2 SYMPTOM QUESTIONNAIRE

Subjects will be asked to rate each of the following DED symptoms (OU), over the last 24 hours, each on a separate VAS: ocular discomfort (ODS), eye dryness (EDS), [REDACTED] For each VAS, subjects will be asked to place a vertical mark on the horizontal line to indicate the level of each symptom, with 0 corresponding to "No Symptom" and 100 corresponding to "Maximal Symptom". The assessment line length of the scale will be 100 mm and will be similar to the following depiction (Figure 4). The questionnaire will be administered at Screening, Baseline (Day 1), and Days 7, 14, 28, and 90. The ODS, EDS, [REDACTED] scores will be summarized separately.

[figure not shown]

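### The symptom ANCOVAs adjust only for the Day 1 score; adding the Screening score already collected on the same instrument would cost almost nothing and may narrow the intervals

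*SAP*

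**What the plan says.** The protocol and the SAP use essentially the same model for change from baseline. Protocol 9.5.4 has changes "analyzed using an ANCOVA model with terms for Baseline value, treatment, and site". SAP 13.5 has them "analyzed using an analysis of covariance (ANCOVA) model with terms for baseline value, treatment, and analysis center".

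SAP 8.4 identifies the covariate: "The efficacy endpoint baseline will be the Baseline (Day 1) measurement". It also rules that "Screening visit and unscheduled visit measurements if any prior to the initiation of randomized study intervention" may not serve as the efficacy baseline, even when the Day 1 value is missing.

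A second pre-randomization reading is planned. SAP 13.2.1 states "The SANDE will be administered at Screening, Baseline (Day 1), and Days 7, 14, 28, and 90". For the ODS and EDS scales, SAP 13.2.2 states "The questionnaire will be administered at Screening, Baseline (Day 1), and Days 7, 14, 28, and 90".

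For two of the scores the Screening reading is also an entry requirement. The protocol synopsis requires a score of at least 50 "based on SANDE (Symptoms Assessment iN Dry Eye) at both the Screening and Baseline visits" and at least 50 "based on Ocular Discomfort Score (ODS) assessed on a Visual Analog Scale (VAS) at both the Screening and Baseline visits". The visible criteria contain no such requirement for EDS or for the SANDE frequency and severity sub-scores.

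SAP 2.1.2 lists six symptom endpoints of this kind: global SANDE at Days 28 and 90, and SANDE frequency, SANDE severity, EDS and ODS at Day 90.

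**The concern.** A single mark on a visual analog scale is a noisy reading of how a subject usually feels. A second reading on the same instrument before randomization carries further information about that level. Used as a covariate, it can explain part of the follow-up variance that the Day 1 score leaves unexplained. The trial collects this reading in any case.

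What is at stake is the width of the confidence intervals. The protocol synopsis tests the secondary endpoints in a fixed sequence, so a narrow miss on a symptom endpoint could block those after it.

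**Working it through.** **1. The plan's own figure.** Inputs from Protocol 9.2 and SAP 5: 202 per arm, SD 17.72, two-sided alpha 0.05, and a SANDE Day 28 difference of -7.9 (protocol) or -8.3 (SAP).

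- Standard error = 17.72 × √(2/202) = 1.763.
- Power at 7.9: 7.9/1.763 = 4.48; 4.48 − 1.96 = 2.52; power 99.4%.
- Power at 8.3: 8.3/1.763 = 4.71; 4.71 − 1.96 = 2.75; power 99.7%.

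The stated 99% reproduces under either difference.

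**2. Variance reduction from adding Screening.** Let r = 1 − (residual variance with Day 1 and Screening)/(residual variance with Day 1 only). Everything below is assumed, because the documents give no between-visit correlations. In each model, simulated subjects had to score 50 to 100 at both Screening and Day 1.

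- *Stable true score plus independent visit errors.* Mean 68, SD of change 17.72. For (true SD, error SD) of (10, 6), (15, 8), (15, 10), (12, 12) and (10, 10), r is about 3.2%, 5.4%, 6.5%, 5.4% and 4.3%.
- *The same five settings, with the true score's correlation falling at each step (Screening to Day 1, Day 1 to follow-up).* At 0.9 per step r is 1.7 to 3.5%; at 0.8, 0.9 to 2.0%; at 0.7, 0.5 to 1.1%.
- *Equal correlations among Screening, Day 1 and follow-up, before the entry cut.* Mean 60 or 70, SD 20. At correlations of 0.3, 0.5, 0.6, 0.7 and 0.8, r is about 2%, 6%, 8%, 11% and 14 to 15%.
- *Decaying correlations in that second model.* For example 0.7 (Screening with Day 1), 0.7 (Day 1 with follow-up) and 0.5 (Screening with follow-up): r is 0 to 1%.

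**3. What that buys.** Treat 17.72 as the residual SD, itself an assumption, and multiply it by √(1 − r). The 95% half-width is 1.96 × 17.72 × √(2/202) × √(1 − r). The equivalent extra subjects are 460 × (1/(1 − r) − 1).

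| r | Half-width (points) | Power at -7.9 | Equivalent extra subjects on 460 |
|---|---|---|---|
| 0% | 3.46 | 99.4% | 0 |
| 1% | 3.44 | 99.4% | 5 |
| 3.2% | 3.40 | 99.5% | 15 |
| 6.5% | 3.34 | 99.6% | 32 |
| 14.6% | 3.19 | 99.8% | 79 |

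The number per arm needed for 99% power at -7.9 falls from 185 to between 158 and 185.

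No difference is stated for the Day 90 endpoints. As an illustration with the same SD and 202 per arm, an r of 3.2 to 6.5% moves power at a true difference of 4 from about 62% to 63–65%, and at 5 from about 81% to 82–83%.

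**4. Validity.** In 4,000 simulated trials per setting (equal correlation 0.6, both readings cut at 50):

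- *Day 1 only:* mean estimate -7.90 for a true -7.9; type I error 4.8%.
- *Day 1 plus Screening:* mean estimate -7.92; type I error 4.5%.

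Monte Carlo error on a 5% rate is √(0.05 × 0.95/4000) = 0.34 points, so both rates are consistent with 5%. The empirical standard error fell from 1.541 to 1.481 under no effect (3.9%) and from 1.579 to 1.471 under -7.9 (6.8%).

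**The case against.** The strongest reply is that nothing here is an error. ANCOVA on the last value before treatment is a standard model, the protocol and SAP agree on it, and it is valid. That stands: this is an optional refinement.

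The second reply is that the gain may be close to nothing, and the design gives reasons to expect decay. Subjects take vehicle twice daily between Screening and Day 1, so Screening is a reading before vehicle while Day 1 and follow-up are readings on drops. Artificial tears are allowed until 2 hours before Screening but not during the study. Day 90 is about 104 days after Screening. This also stands. The 3 to 6.5% range, and the 15 to 32 subjects it implies, depend on a stable true score and are not bounds in either direction.

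Third, SANDE Day 28 is already powered at 99%, and half a point or less of added power will not change a conclusion. That is right for this endpoint at the planned difference. It does not settle the Day 90 endpoints.

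A reader might infer a stronger fault: that selecting on Day 1 scores of at least 50 distorts the baseline and so undermines all the symptom comparisons. The documents do not support this.

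- The cut comes before randomization and applies to both arms, so regression to the mean does not bias the treatment difference.
- It acts directly only on global SANDE and ODS. EDS has no visible cut. The sub-scores are restricted only indirectly: √(frequency × severity) ≥ 50 with each at most 100 forces each to be at least about 2500/100 = 25.
- The Screening SANDE and ODS scores are cut at 50 as well, so Screening is not an untruncated alternative. The case rests on repeat measurement, not on truncation.

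Nor can a reader conclude that the SAP ignores Screening everywhere. Text after the ANCOVA sentence is redacted and the imputation details are not visible, so the omission is confirmed only for the visible model.

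**Conclusion.** The point holds as a low-cost gain in precision, not as a flaw in validity. The visible SAP 13.5 model leaves out a pre-randomization score that is scheduled for all six symptom endpoints and required for entry on global SANDE and ODS.

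The plausible variance reduction runs from essentially zero to about 15%, and the documents cannot narrow it. The conclusion does not need a particular figure within that range: the covariate is measured before randomization, so it cannot bias the comparison, and the worst case is one degree of freedom spent for almost no gain. Any benefit would show mainly as narrower intervals at Day 90. It is worth doing if the SAP is opened, and it is not a reason to question the planned analysis.

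**What to change.** Before unmasking, amend SAP 13.5 for SANDE (global, frequency and severity), ODS and EDS:

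- Add the Screening value of the same score as a pre-specified covariate alongside the Day 1 value, giving Day 1 value, Screening value, treatment and analysis center.
- Keep Day 1 as the baseline for computing change. SAP 8.4 can stay as it is, because a covariate does not redefine baseline.
- Include the Screening value in the imputation model for these endpoints if the redacted text does not already do so.
- State a simple rule for a missing Screening EDS value, since EDS is scheduled but is not an entry criterion in the visible text.

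The cost is one model term, one degree of freedom, a few lines of SAP text and the matching programming. No new data are needed.

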## **14. Safety Analyses**

All safety analyses will be conducted using the Safety population.

### **14.1 Adverse Events**

An AE is defined as any untoward medical occurrence associated with the administration of the study intervention in humans, whether or not considered to be related to the study intervention. Any medical condition present prior to informed consent which remains unchanged or improved should not be recorded as an AE at subsequent visits. Any pre-existing medical condition that worsens after first administration of the study intervention will also be considered a new AE. AEs should be documented

from the time the subject provides informed consent until subject participation in the study has been completed. All AEs will be coded using MedDRA Version 25.0.

Treatment-emergent adverse events (TEAEs) are defined as any event that occurs or worsens on or after the day that randomized study intervention is initiated. Only TEAEs will be included in the summary tables by treatment group, but all AEs will be included in the subject listings.

Severity of an AE (mild, moderate, and severe) is defined as a qualitative assessment of the degree of intensity of an AE as determined by the Investigator or reported to him/her by the subject. The relationship of each AE (not related, unlikely related, possibly related, and related) to the study intervention and the expectedness of each AE (unexpected and expected) should be determined by the Investigator.

An overall summary will be presented that includes the number of events and the number and percentage of subjects who experienced at least one event for the following: TEAEs, serious TEAEs, serious TEAEs related to study intervention. TEAEs will also be classified by strongest relationship to study intervention (not related, unlikely related, possibly related, or related) and by maximum severity (mild, moderate, or severe). The number and percentage of subjects with a TEAE leading to study intervention discontinuation and with a TEAE leading to death will also be summarized. In addition, similar overall summaries for ocular TEAEs and non-ocular TEAEs will be presented.

Additional TEAE summaries will be produced showing the number and percentage of subjects who experienced at least one TEAE. These summaries will be presented by SOC and PT. If a subject reports the same PT multiple times within the same SOC, that PT will only be reported once within that SOC. If a subject reports multiple conditions within the same SOC, that SOC will only be reported once. SOCs and PTs within each SOC will be listed in order of descending frequency for 0.003% AR-15512.

Separate summaries will be provided for the following categories of TEAEs:

- TEAEs
- Ocular TEAEs
- Non-Ocular TEAEs
- Ocular treatment-related TEAEs
- Non-Ocular treatment-related TEAEs
- Serious TEAEs
- Ocular serious TEAEs
- Non-Ocular serious TEAEs
- Ocular TEAEs leading to study intervention discontinuation
- Non-Ocular TEAEs leading to study intervention discontinuation

Summaries of TEAEs by maximum severity and summaries of TEAEs by the strongest relationship to the study intervention will be presented for ocular AEs and non-ocular AEs separately. The number of subjects with any TEAEs (along with percentages) will be tabulated by SOC and PTs within each SOC by treatment

group. To count the number of subjects with any TEAEs, if a subject has multiple TEAEs coded to the same SOC or PT within the same SOC, the subject will be counted once under the maximum severity or strongest relationship.

All AEs will be presented in a subject listing. The SAEs, AEs leading to study intervention discontinuation, AEs leading to death will be listed separately.

#### **14.2 Clinical Laboratory Data**

Clinical laboratory data including hematology, coagulation, and urinalysis will be collected at Baseline (Day 1), and Day 90 or ET. Overall clinical laboratory results at each visit will be reviewed and be interpreted as normal, abnormal, NCS (non-clinically significant), and abnormal, CS (clinically significant). Abnormal, CS results will be specified.

The actual and change from baseline in laboratory test results will be summarized using continuous descriptive statistics for each treatment group. The interpretation of results relative to the reference range (low panic, low normal, normal, high normal, high panic, abnormal) will be summarized using counts and percentages for each treatment group. Shift tables for the interpretation of results relative to the reference range will be provided comparing baseline with Day 90.

Subject listings of laboratory results (hematology, coagulation, and urinalysis) will be produced. When deemed necessary, manual differential results may be collected, which will be listed in the subject listing for hematology. Urine microscopic results may be collected when abnormal urinalysis results are observed, which will be listed in the subject listing for urinalysis. In addition, the overall laboratory results review and interpretation at each visit will be presented in a separate listing.

#### **14.3 Vital Signs**

Vital signs (sitting heart rate in beats/min and sitting blood pressure in mmHg [systolic and diastolic blood pressure]) will be assessed at Screening, Baseline (Day 1), and Day 90 or ET.

The actual and change from baseline in vital signs will be summarized using continuous descriptive statistics by visit for each treatment group. A subject listing of visual acuity will be produced.

#### **14.4 Corrected Visual Acuity**

The logarithm of the minimum angle of resolution (logMAR) visual acuity in both eyes will be assessed using an Early Treatment of Diabetic Retinopathy Study (ETDRS) Series 2000 chart at Screening, Baseline (Day 1), and Days 7, 14, 28, 90, or ET.

The actual and change from baseline in logMAR will be summarized for each eye (study eye and fellow eye) using continuous descriptive statistics by visit for each treatment group. The actual and changes from baseline to maximum on-treatment value (i.e. the worst on-treatment) will be summarized as well. The maximum on-treatment value is the highest logMAR value for each subject and eye from all post-baseline scheduled or unscheduled visits. In addition, change from baseline categories will be summarized using counts and percentages including the following categories: <= 0, >0 to <=0.09, >= 0.10 to <=0.19, >=0.20 to <=0.29, and >=0.30 for each eye (study eye and fellow eye) by visit and for each treatment group. A subject listing of corrected visual acuity will also be produced.

#### **14.5 Slit-Lamp Biomicroscopy**

A slit-lamp biomicroscopy examination of the lids (erythema and edema), conjunctiva (hyperemia and edema), cornea (edema, staining/erosion), anterior chamber (cells, flare), iris, and lens (lens opacity for phakic only), will be performed at Screening, Baseline (Day 1), Days 7, 14, 28, 90, or ET. The findings are graded for clinical significance as clinically significant (CS) and non-clinically significant (NCS).

A shift table of score values will be provided comparing each follow-up visit to the baseline. A subject listing of slit-lamp biomicroscopy will also be produced.

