## **9.6 Safety Endpoints and Analyses**

Adverse events will be coded using the MedDRA dictionary. Frequencies and percentages of treatment-emergent adverse events will be summarized at the subject level by system organ class and preferred term for all TEAEs, treatment related TEAEs, serious TEAEs, and TEAEs causing premature discontinuation of study drug by treatment group. An AE is treatment emergent if it occurs or worsens after the first dose of trial treatment. Similar summaries will be presented for all TEAEs by maximal severity. Separate summaries will be performed for ocular and non-ocular TEAEs.

Other safety endpoints including visual acuity, slit-lamp biomicroscopy, and dilated fundoscopy will be summarized by treatment group and visit using descriptive statistics. Changes or shifts from Baseline will also be summarized where appropriate. For assessments performed by eye, study eye and fellow eye will be summarized separately.

In addition, changes from Baseline to worst on-treatment value for ocular safety assessments will be summarized.

[figure not shown]

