Table 14.3.2.2.3	Urinalysis Results by Visit	Safety Population
Table 14.3.2.3.1	Shift in Hematology from Baseline to Day 90	Safety Population
Table 14.3.2.3.2	Shift in Chemistry from Baseline to Day 90	Safety Population

Table Number	Title	Population
Table 14.3.2.3.3	Shift in Urinalysis from Baseline to Day 90	Safety Population
Table 14.3.3	Actual and Change from Baseline in Vital Signs by Visit	Safety Population
Table 14.3.4.1	Actual and Change from Baseline in Corrected Visual Acuity in logMAR Score by Visit	Safety Population
Table 14.3.4.2	Categorical Analysis of Change from Baseline in Corrected Visual Acuity logMAR Score by Visit	Safety Population
Table 14.3.5.1	Shift in Slit-Lamp Biomicroscopy Results by Visit – Study Eye	Safety Population
Table 14.3.5.2	Shift in Slit-Lamp Biomicroscopy Results by Visit – Fellow Eye	Safety Population
Table 14.3.6	Actual and Change from Baseline in Intraocular Pressure (mmHg) by Visit	Safety Population
Table 14.3.7.1	Shift from Baseline in Dilated Fundus Exam Results to Day 90 – Study Eye	Safety Population
Table 14.3.7.2	Shift from Baseline in Dilated Fundus Exam Results to Day 90 – Fellow Eye	Safety Population

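### The SAP gives slit-lamp biomicroscopy no baseline-to-worst summary, so its planned tables leave the share of subjects who ever worsen undetermined

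*SAP*

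**What the plan says.** Protocol 9.6 makes two commitments for safety data other than adverse events. The first names the slit-lamp exam: "Other safety endpoints including visual acuity, slit-lamp biomicroscopy, and dilated fundoscopy will be summarized by treatment group and visit using descriptive statistics". The second closes the section and covers a class of assessments: "In addition, changes from Baseline to worst on-treatment value for ocular safety assessments will be summarized".

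The SAP then treats the ocular assessments one at a time:

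- **Visual acuity (14.4).** The worst-value summary is kept: "The actual and changes from baseline to maximum on-treatment value (i.e. the worst on-treatment) will be summarized as well". Its source is defined: "The maximum on-treatment value is the highest logMAR value for each subject and eye from all post-baseline scheduled or unscheduled visits".
- **Slit-lamp (14.5).** The exam "will be performed at Screening, Baseline (Day 1), Days 7, 14, 28, 90, or ET". The planned summary is: "A shift table of score values will be provided comparing each follow-up visit to the baseline". No worst value is mentioned. Tables 14.3.5.1 and 14.3.5.2 cover the study eye and the fellow eye.
- **Intraocular pressure (14.6) and dilated fundus exam (14.7).** These too have by-visit or baseline-to-follow-up summaries only. Each has one scheduled post-baseline exam, at Day 90.

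Two general rules apply. SAP 8.5 confines ET and unscheduled visits to the listings. SAP 1 states that its statistical methods take precedence over those in the protocol.

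**The concern.** For a drop given twice daily, the slit-lamp exam is where lid, conjunctival and corneal changes are recorded. Such changes may come and go, and may appear at different visits in different subjects. A natural safety question is how many subjects in each arm worsened at any time on treatment. A baseline-to-worst shift answers it in one count. Four cross-sectional shift tables do not, because they do not show whether the subjects counted at Day 7 are those counted at Days 14, 28 and 90.

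The protocol appears to have foreseen this and promised the worst-value summary on top of the by-visit one. Because the SAP takes precedence, its narrower plan is the one that would be run. Visual acuity would then have a worst-value summary that includes unscheduled visits, while the slit-lamp exam would have none.

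**Working it through.** The plan states no slit-lamp rate, so there is no figure to reproduce. The check compares the texts and then works out what by-visit tables can determine.

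**Texts side by side**

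| Assessment | Scheduled post-baseline exams | Worst value in protocol 9.6 | Worst value in SAP |
|---|---|---|---|
| Visual acuity | Days 7, 14, 28, 90 | yes, as an ocular safety assessment | yes (14.4) |
| Slit-lamp | Days 7, 14, 28, 90 | yes, on the natural reading | no (14.5) |
| Intraocular pressure | Day 90 | yes, on the natural reading | no (14.6) |
| Dilated fundus exam | Day 90 | yes, on the natural reading | no (14.7) |

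With one scheduled exam, the by-visit result and the worst scheduled result coincide. For pressure and fundus the loss is therefore confined to ET and unscheduled values. For slit-lamp it also touches subjects who complete the study.

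**What four by-visit tables determine**

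Inputs: 4 scheduled post-baseline exams (SAP 14.5); 230 subjects per arm (SAP 5), taken for simplicity as all examined at each visit; and an assumed share p of the arm worsened from Baseline at each visit. The documents give no value for p, so a range is shown.

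- Lower limit, the same subjects at every visit: ever worsened = p.
- Upper limit, different subjects at every visit: ever worsened = min(1, 4p).
- Reference case, independence between visits: 1 − (1 − p)^4.

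| Assumed p | Lower limit | Independence | Upper limit |
|---|---|---|---|
| 2% | 2% (4.6 of 230) | 7.8% (17.9) | 8% (18.4) |
| 5% | 5% (11.5) | 18.5% (42.7) | 20% (46.0) |
| 10% | 10% (23.0) | 34.4% (79.1) | 40% (92.0) |

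Worked line for 5%: 1 − 0.95^4 = 1 − 0.8145 = 0.1855; 230 × 0.1855 = 42.7; 4 × 0.05 = 0.20; 230 × 0.20 = 46. In each row the upper limit is four times the lower. Two arms with identical by-visit margins could thus differ up to fourfold in subjects who ever worsen.

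**Does this imply a direction between arms?** Take 5% against 2% per visit, with independence in both arms. The ratio per visit is 5/2 = 2.50, and the ratio ever worsened is 18.55/7.76 = 2.39. The difference goes from 3 points to 18.55 − 7.76 = 10.8 points. The absolute gap grows while the relative one shrinks slightly. With full persistence in both arms nothing changes. No direction is established.

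**The case against.** **The promise may not reach the slit-lamp exam.** Protocol 9.6 mentions changes and shifts separately and then uses only changes in the worst-value sentence. Slit-lamp findings are graded categories reported as shifts, so the SAP might be read as applying the sentence where a numeric change makes sense. This is arguable. However, the sentence names the plural class of ocular safety assessments, shortly after naming slit-lamp. The numeric reading would also take in intraocular pressure, which has no worst-value summary either.

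**Redaction.** Parts of the SAP are blacked out, including text directly after the rule on ET and unscheduled visits. An explanation there cannot be excluded. The visible rule in 14.5 is nevertheless complete in itself.

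**Other outputs help.** The ocular treatment-emergent adverse event tables count each subject once over the treatment period, also by maximum severity. Protocol 7.4 requires adverse events at unscheduled visits to be recorded. Listing 16.2.10.2 holds the subject-level exams, and SAP 1 allows supplementary analyses. All of this stands, but the cover is partial. Under protocol 6.9.3.1, signs that fit the expected course of dry eye disease are not reportable adverse events, and a listing gives no count by arm.

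**Readings that go too far.**

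- A reader might infer that findings from unscheduled visits are lost altogether. They are missing only from the slit-lamp tables.
- A reader might take the by-visit wording of titles such as "Shift in Slit-Lamp Biomicroscopy Results by Visit – Study Eye" as proof that no worst-value block is planned. It is not proof: visual acuity Table 14.3.4.1 has the same wording, although 14.4 requires the worst value. The point rests on the silence of 14.5.
- A reader might call slit-lamp the only structural eye exam repeated on treatment. The visit lists contain redacted procedures, so this cannot be verified.

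**Conclusion.** The point holds as a gap in a descriptive safety summary and a misalignment between protocol and SAP. The protocol's worst-value commitment survives in the visible SAP for visual acuity only. Slit-lamp is where the omission counts most, because it has four scheduled post-baseline exams. The planned slit-lamp tables leave the ever-worsened share undetermined: at an assumed 5% per visit it could be 5% to 20%, about 12 to 46 of 230 per arm. The per-visit rate is an assumption. The range itself does not need independence, and the gap is zero if the same subjects are affected each time.

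A reader might infer that the comparison between arms is understated. The documents do not support that. Both arms are tabulated alike, and the effect on the contrast depends on how persistent findings are in each arm, which is unknown. The contrast in ever-worsened subjects is undetermined, not biased in a known direction.

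No endpoint, test or data collection is affected. This is a cheap improvement.

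**What to change.** In SAP 14.5 and Tables 14.3.5.1 and 14.3.5.2, add a shift from Baseline to the worst post-baseline grade, by structure and by eye. Use the order normal, abnormal not clinically significant, abnormal clinically significant, which follows from protocol 6.8.3 and SAP 14.5. Take the worst grade over all scheduled, unscheduled and ET exams, and state this as an explicit exception to SAP 8.5. SAP 14.4 already draws on unscheduled visits for logMAR; ET should be named outright. Keep the by-visit shifts.

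The exams are already collected, so the cost is one sentence in the SAP and one extra block in two existing tables. The downside is that the slit-lamp figures may look slightly less favourable, since an ever-worsened count cannot be lower than the count at any single visit.
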